**Table 10 Adverse Event Definitions**

	Definition
Treatment-emergent adverse event (TEAE)	Treatment-emergent AEs are defined as AEs with onset on or after the first administration of IMP
Treatment Related AE	Any AE reported by the investigator as treatment related (ie, “Relationship to ARGX-117/Placebo= Related” in the CRF “Adverse event” page) and those of missing relationship.
IVIg Related AE	Any AE reported by the investigator as IVIg related (ie, “Relationship to IVIg treatment= Related” in the CRF “Adverse event” page) and those of missing relationship.
Procedure Related AE	Any AE reported by the investigator as procedure related (ie, “Relationship to any study procedure = Related”) and those of /missing relationship.
Serious Adverse Events (SAEs)	Any AE with “Is this a serious adverse event?” = Yes in the CRF “Adverse event” page.
Non serious Adverse Events	Any AE with “Is this a serious adverse event?” = No in the CRF “Adverse event” page.
Adverse Events Leading to Interruption of IMP	Any AE with “ARGX-117/Placebo interrupted?” = Yes in the CRF “Adverse event” page.
Adverse Events Leading to Permanent Treatment Discontinuation	Any AE with “ARGX-117/Placebo withdrawn” = Yes in the CRF “Adverse event” page.
Adverse Events Leading to Death	Any AE with fatal outcome or AE with NCI CTCAE grade = 5
Adverse Event of Special Interest	AESIs are defined as events with grade ≥ 3 and a PT that falls under the MedDRA SOC Infections and infestations.
Adverse Event of Hypersensitivity Reactions	Any AE with PT from SMQ (narrow) selection for hypersensitivity reaction
Adverse events of Anaphylactic Reaction	Any AE with PT from SMQ (narrow) selection for anaphylactic reaction
Adverse Events of Local Reactions	Any AE with MedDRA PT in the MedDRA High Level Group Term of administration site reactions, regardless of time of onset.

Summary tables of TEAEs will be presented for the DBTP (SAF set).

AE will also be allocated to the first period that is possible based on the available part of the AE start and stop date/time. If, for a participant not entering the safety follow-up period or LTE, an AE occurs following V14 or treatment discontinuation, then the AE will be counted in the DBTP.

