**Table 17 Participant Classification for ADA Against ARGX-117**

	Highest c post baseline sample status				
Baseline ADA sample status	ADA negative	ADA positive (missing titer a )	ADA Positive (negative titer b or numerical titer value)		ADA Unevaluable
ADA negative	ADA negative	Treatment-induced ADA	Treatment-induced ADA		ADA Unevaluable
ADA positive (missing titer a )	Treatment-Unaffected ADA	ADA Unevaluable	ADA Unevaluable		ADA Unevaluable
ADA Positive (negative titer b or numerical titer value)	Treatment-Unaffected ADA	ADA Unevaluable	titer < 4 x baseline titer: Treatment-Unaffected ADA	titer ≥ 4x baseline titer: Treatment-Boosted ADA	ADA Unevaluable
ADA Unevaluable	ADA Unevaluable	ADA Unevaluable	ADA Unevaluable		ADA Unevaluable

a Samples with missing titer have as reported ADA result ‘positive immuno-depletion’ or ‘positive titer’;

b Results reported as ‘negative titer’, ie, titer value < 100 will be set to 100

c Highest sample status, with order: (from low to high) : ADA unevaluable, ADA negative, ADA positive (missing titer /positive immuno-depletion), ADA positive with titer<100 (‘negative titer’) as reported ADA result, titer value set to 100), ADA positive with titer≥100 (ie, numerical value selecting the sample with highest titer)

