**ADA evaluable participant = participant classified as any of following categories according to**

**Table 17:** ADA negative, treatment-unaaffected ADA, treatment-induced ADA, treatment-boosted ADA.  
The first 2 categories are classified as ‘ADA negative’, the latter 2 as ‘ADA positive’.

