**ADA unevaluable participant = participant classified as ADA unevaluable according to**

Table 17 or with missing baseline ADA sample or without postbaseline ADA samples

Note: Fourfold difference in titer values is considered significant in case a twofold serial dilution is applied (= 2 times the dilution factor) (reference to Shankar et al., 2014).

The ADA incidence is defined as the percentage of participants with treatment-induced ADAs or treatment-boosted ADAs among the number of evaluable participants.

The ADA prevalence is defined as the percentage of participants with ‘treatment-unaaffected ADA’, ‘treatment-induced ADA’ or ‘treatment-boosted ADA’ among the number of evaluable participants.

ADA analysis will be performed in the SAF set, combining data from DBTP and safety FU.

Frequency tabulations (Number and percentages) will be provided with ADA negative/positive/unevaluable samples per analysis visit and per ADA against ARGX-117 participant classification for each following treatment groups:

- ARGX-117 Dose Regimen 1
- ARGX-117 Dose Regimen 2 [REDACTED] if applicable
- ARGX-117 Dose Regimen 3 [REDACTED] if applicable
- Total ARGX-117
- Total Placebo

Frequency tabulations (Number and percentages) will be provided by treatment group and ARGX-117 combined on:

- Participants per ADA participant classification
- Prevalence and incidence of ADA
- ADA unevaluable participants
- ADA baseline positive / negative / unevaluable samples

ADA titer values against ARGX-117 will be summarized using descriptive statistics by ADA participant classification.

All immunogenicity data will be listed.

Correlation tables by ADA participant classification against ARGX-117 will be provided for the following parameters:

- Serum ARGX-117 concentration over time
- Concentration of free C2
- Percent change from baseline in free C2
- Concentration of total C2
- Percent change from baseline in total C2
- Concentration of CH50
- Percent change from baseline in CH50

- Overall Treatment-Emergent Adverse Events by MedDRA System Organ Class and Preferred Term by Overall Antidrug Antibodies Participant Classification (All Patients)
- Overall Serious Treatment-Emergent Adverse Events by MedDRA System Organ Class and Preferred Term by Overall Antidrug Antibodies Participant Classification (All Patients)
- Overall Treatment-Emergent Hypersensitivity reaction(as defined in the 6.4.1 section) by Overall Antidrug Antibodies Participant Classification (All Patients)

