- c Participants who demonstrate a clinical deterioration during the DBTP may be re-treated with IVIg. A UNS IVIg visit will be performed at the participant's first occurrence of clinical deterioration necessitating retreatment with IVIg. If the timing for subsequent IVIg retreatment does not coincide with a regularly scheduled visit day of the DBTP, a UNS visit will be performed for the participant to receive IVIg.
- d A UNS visit can occur at the request of the investigator and additional assessments can be performed at the discretion of investigator. (X) indicates that the assessment will be performed at the discretion of the investigator.
- e A urine pregnancy test will be performed at V1, V6, V8, V11, V12, V14/ED and at any UNS visits for women of childbearing potential.
- f The PE will include the parameters specified in Section 8.2.1 of the protocol.
- g The weight measured at IMV3 will be used to calculate the dose for all IMP administrations.
- h Triplicate 12-lead ECGs will be performed during screening and at V1. A single 12-lead ECG will be performed at all other scheduled time points.
- i The C-SSRS will be used to assess the risk of suicidal ideation at screening. SIB risk monitoring will be based on question 9 of the PHQ-9 at all other scheduled time points.
- j An ANA test will be performed at the specified time points, the titer and staining pattern will be reported; the potential presence of ENA autoantibodies (anti-dsDNA, anti-Smith, anti-phospholipid (anti-cardiolipin IgG and anti-beta-2-glycoprotein IgG), anti-Ro (anti-Ro52 and anti-Ro60), anti-La and anti-U1RNP) will be evaluated from the blood samples collected. The presence of ENA autoantibodies will only be reported if ANA  $\geq$ 1:100.
- k PK and PD assessments on day 1 will be performed predose, 2 hours, and 6 hours postdose of the IMP infusion. Detailed schedules for collecting blood samples for PK and PD analyses are provided in Table 4 and Table 5.
- l A detailed schedule for collecting blood samples for cytokine analyses is provided in [Table 23](#).
- m Immunogenicity assessments will be performed predose of IMP administration.
- n [REDACTED]
- o Sample collection is optional.
- p Samples must be collected predose on days when IMP or IVIg are administered.
- q IVIg will be administered to participants demonstrating a meaningful clinical deterioration.

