Table	14.2.2.3	Individual Values and Descriptive Statistical Summary: Serum Concentrations Following Administration of EMPASIPRUBART - PK Set		x	x
PHARMACODYNAMICS					
Table	14.2.3.1	Summary of Free C2 Concentrations <unit> during IMVP and DBTP - PD set		x	x
Table	14.2.3.3	Summary of Total C2 Concentrations <unit> during IVMP and DBTP - PD set		x	x
Table	14.2.3.5	Summary of CH50 Concentrations <unit> during IVMP and DBTP - PD set		x	x
IMMUNOGENICITY					
Table	14.2.4.1	ADA against EMPASIPRUBART Classification by Visit during DBTP and Safety Follow-up Period - Safety Set		x	x
Table	14.2.4.2	Incidence and Prevalence of ADA against EMPASIPRUBART during DBTP and Safety Follow-up Period - Safety Set		x	x
Table	14.2.4.3	Summary of ADA against EMPASIPRUBART Titer Values by ADA Participant Classification against ARGX-117 by Visit during DBTP and Safety Follow-up Period - Safety Set		x	x
Table	14.2.4.4	Empasiprubart concentration over time by ADA participant classification against EMPASIPRUBART - <Treatment Group> - PK Set		x	x
Table	14.2.4.5	Free C2 concentrations over time by ADA participant classification against Empasiprubart - <Treatment Group: > - PD Set		x	x
Table	14.2.4.6	Percent change from baseline in free C2 by ADA participant classification against Empasiprubart - <Treatment Group> - PD Set		x	x

Table	14.2.4.7	Total C2 concentrations over time by ADA participant classification against Empasiprubart - <Treatment Group> - PD Set		x	x
Table	14.2.4.8	Percent change from baseline in total C2 by ADA participant classification against Empasiprubart - <Treatment Group> - PD Set		x	x
Table	14.2.4.9	CH50 concentrations over time by ADA participant classification against Empasiprubart - <Treatment Group> - PD Set		x	x
Table	14.2.4.10	Percent change from baseline in functional complement activity (CH50) by ADA participant classification against Empasiprubart - <Treatment Group> - PD Set		x	x
Table	14.2.4.11	Overall Treatment-Emergent Adverse Events by MedDRA System Organ Class and Preferred Term by Overall Antidrug Antibodies Participant Classification - <Treatment group> - Safety Set		x	x
Table	14.2.4.12	Overall Serious Treatment-Emergent Adverse Events by MedDRA System Organ Class and Preferred Term by Overall Antidrug Antibodies Participant Classification - <Treatment group> - Safety Set		x	x

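### The AE tables by final ADA class (14.2.4.11 to 14.2.4.15) do not separate events before ADA conversion from events after it

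*SAP*

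**What the plan says.** Table 17 of the SAP gives each participant one ADA class by crossing the baseline sample status with the highest post-baseline status; its footnote c sets the ranking ("Highest sample status, with order: (from low to high"). On the period covered, section 6.6.3 states: "ADA analysis will be performed in the SAF set, combining data from DBTP and safety FU". One qualifying sample at any time is enough.

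That fixed class then defines the outputs. Section 6.6.3 announces: "Correlation tables by ADA participant classification against ARGX-117 will be provided for the following parameters". The list covers serum concentration, free C2, total C2, CH50, all TEAEs, serious TEAEs, and hypersensitivity, anaphylactic and local reactions. For hypersensitivity it reads "Overall Treatment-Emergent Hypersensitivity reaction(as defined in the 6.4.1 section) by Overall Antidrug Antibodies Participant Classification (All Patients"). In Table 24 these are Tables 14.2.4.4 to 14.2.4.15. The concentration tables are laid out over time ("Empasiprubart concentration over time by ADA participant classification"); the AE tables, 14.2.4.11 to 14.2.4.15, are not.

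The event window is in Table 10: "Treatment-emergent AEs are defined as AEs with onset on or after the first administration of IMP". On sampling, a footnote to Table 19 states: "Immunogenicity assessments will be performed predose of IMP administration".

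**The concern.** No visible rule compares the onset of an event with the date of the first sample that makes a participant treatment-induced or treatment-boosted. Take a participant who is ADA negative at baseline, reacts at the first infusion, and first tests positive at V14. That reaction is tabulated under treatment-induced ADA, although it preceded every positive sample. For a boosted participant, who already had ADA at baseline, the same applies to events before the titer rose.

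The AE tables show no timing, so a reader cannot see this. Safety is the primary objective and only 16 participants per arm are planned, so one reaction can change how such a table reads. The main risk is that a real link between ADA and reactions is flattened.

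**Working it through.** The SAP gives no figure for this point, so there is nothing to reproduce. The check traces the derivation and then illustrates the size.

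**Tracing**

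- Class: baseline sample and highest post-baseline sample (Table 17), over both periods (section 6.6.3).
- Events: all from first dose (Table 10).
- ADA samples: scheduled visits V1, V4, V6, V8, V11 and V14, plus unscheduled visits (Table 19); FUV2 to FUV6, weeks 12 to 64 of follow-up (Table 20).
- Time-resolved ADA outputs: classification by visit (14.2.4.1) and titer by visit (14.2.4.3). Neither is joined to AEs.
- No before/after-ADA split appears in the visible text or in Table 24. Some text after the list in section 6.6.3 is blacked out and cannot be checked.

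**Dilution with equal follow-up**

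Assumptions: 16 weeks for everyone, constant AE rate, conversion at the first positive sample in week t, true rate ratio RR afterwards.

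Share of time before conversion = t/16. Rate ratio shown by final class = (t + RR × (16 − t))/16.

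| t (weeks) | Share before | Shown if RR = 2 | Shown if RR = 3 |
|---|---|---|---|
| 2 | 12.5% | 1.88 | 2.75 |
| 4 | 25% | 1.75 | 2.5 |
| 8 | 50% | 1.5 | 2.0 |
| 12 | 75% | 1.25 | 1.5 |
| 16 | 100% | 1.0 | 1.0 |

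Example: t = 8, RR = 3 gives (8 + 3 × 8)/16 = 2.0. With RR = 1 the formula gives 1.0 for every t, so equal follow-up creates no spurious excess.

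**Unequal follow-up**

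Assumptions: AEs unrelated to ADA, constant hazards, tables not restricted to the double-blind period. A share s stays for 16 + 64 = 80 weeks; the rest leave for the extension study at week 16. Take s = 10%, a 16-week ADA risk of 5% and a 16-week AE risk of 10%.

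- 80-week risks: ADA 1 − 0.95^5 = 0.226; AE 1 − 0.90^5 = 0.410.
- AE risk in ADA positive: (0.9 × 0.05 × 0.10 + 0.1 × 0.226 × 0.410)/(0.9 × 0.05 + 0.1 × 0.226) = 0.204.
- AE risk in ADA negative: (0.9 × 0.95 × 0.10 + 0.1 × 0.774 × 0.410)/(0.9 × 0.95 + 0.1 × 0.774) = 0.126.

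Over s = 10% to 20%, ADA risk 5% to 15% and AE risk 10% to 30%, the figures are 19% to 58% in ADA positive against 12% to 39% in ADA negative. With s = 0 they are equal.

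**Why the remedy needs its own denominators**

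Suppose first positivity is equally likely at weeks 2, 4, 8, 12 and 16. The mean share before it is (2 + 4 + 8 + 12 + 16)/(5 × 16) = 42/80 = 52.5%. Keeping only later events in the ADA-positive column, with an unchanged denominator, leaves 47.5% of the expected events when there is no ADA effect, so ADA would look protective. With rates on matching person-time, the null ratio returns to 1 under the same constant-rate assumption.

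**PK and PD**

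If half of the eventual converters have converted by a visit, a true 50% fall after conversion shows as 0.5 × 50% = 25% at that visit. By V14 everyone who converts during the double-blind period has done so, and this dilution is gone.

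**The case against.** These are descriptive tables in an exploratory study of 48 participants with no formal testing. A participant-level class is the right basis for incidence and prevalence. All AEs and all immunogenicity data are listed, so timing can be traced case by case. This stands, and it keeps the point modest; but tracing by hand leaves the comparison out of the planned tables.

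A reader might infer that the plan manufactures an association between ADA and reactions. The documents do not support that in general: with equal follow-up the distortion is dilution. A spurious excess needs unequal follow-up, and the modification history refers to the small number who entered safety follow-up. One route remains. Under section 5.4, participants who stop treatment early go on to follow-up, where they have more chances to test positive, so the number of chances could depend on the event itself.

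The first positive sample is also not ADA onset. Samples are predose and spaced apart, and ADA may have arisen at any time since the previous one. A two-way before/after split would therefore misplace some events. This objection stands and shapes the fix.

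A reader might also infer that the PK and PD tables pool values from before and after conversion. They do not: values sit at their own time points. What remains there is that, at a given visit, participants not yet converted share a column with those who have.

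**Conclusion.** The point holds for the five AE tables: the final class ignores when the event occurred relative to conversion. The likely consequence is attenuation, from slight when conversion is early (3 shown as 2.75 at week 2) to complete when it comes at week 16 (3 shown as 1.0). These sizes rest on assumed conversion times, constant AE rates and equal 16-week follow-up; the SAP gives no conversion times or rates. The documents do not show that a false ADA signal is likely. For PK and PD the gain from a change is smaller. This is a cheap improvement to the safety output, not a flaw that undermines the analysis.

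**What to change.** - Keep the class tables for incidence, prevalence and overview.
- Derive two dates per converter: the first sample that meets treatment-induced or treatment-boosted status, and the last sample before it.
- Add a table for hypersensitivity, anaphylactic and local reactions, and if wanted for all TEAEs and serious TEAEs, in three parts: up to the last sample before conversion; between that sample and the first qualifying one (onset unknown); on or after the first qualifying sample.
- Give each part its own person-time and its rate per 100 PYFU, as section 6.4.1 already defines it. Count ADA-negative participants' time and converters' pre-conversion time as not-yet-positive time.
- In the PK and PD tables by visit, add a presentation by ADA status up to and including that visit.

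Cost: SAP wording, two derived dates and modest programming on data already collected. Downsides: small cells and an interval-censored ADA onset. If reactions cluster at the first infusions, the not-yet-positive rate will be higher for that reason alone, so the rates should be read with the study day of each reaction.

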## 7 CHANGES TO PLANNED ANALYSES

The changes between the protocol-defined statistical analyses and those presented in this statistical analysis plan are the following:

[REDACTED]  
[REDACTED]  
[REDACTED] All participants from cohort 2 will be included in the analysis (even ongoing participants) and will be unblinded.

The following endpoints were added:

[REDACTED]  
■ [REDACTED]  
■ [REDACTED]  
■ [REDACTED]  
■ [REDACTED]  
■ [REDACTED]

[REDACTED]  
■ [REDACTED]  
■ [REDACTED]  
[REDACTED]

[REDACTED]  
■ [REDACTED]

[REDACTED]  
■ [REDACTED]

[REDACTED]  
■ [REDACTED]  
■ [REDACTED]  
■ [REDACTED]  
[REDACTED]

[REDACTED]  
■ [REDACTED]  
■ [REDACTED]  
■ [REDACTED]  
■ [REDACTED]  
[REDACTED]

- [REDACTED]

## Statistical Analysis

[REDACTED]

- [REDACTED]

- [REDACTED]

For mMRC-14, MMN-RODS, and CAP-PRI, ANCOVA were added to estimate treatment effect on these parameters.

Description of placebo groups within each cohort were added, in addition to the pooled placebo group (placebo from cohort 1 and placebo from cohort 2).

Description of the change from baseline before IVIg retreatment by IVIg retreatment group and PGIC category, by cohort and overall were added for the following efficacy endpoints: mMRC-10 sum score, mMRC-14 sum score, average mMRC-14 sum for the 2 most important muscle groups, Grip Strength 3 day moving average (most / less) affected hand, MMN-RODS centile score and CAP-PRI total score.

## 9 APPENDICES

### 9.1 Schedule of Activities

**Table 18** IVIg Dependency and IVIg Monitoring Period Schedule of Activities Through Day –7

	IVIg Dosing Frequency	SCN a	IVIg Dependency b		IVIg Monitoring c		
Visit (Days)		Up to 28 days	IDV1 d	IDV2 b	IMV1 f	IMV2	IMV3
	Q 2 weeks		1	29	1	15	29
	Q 3 weeks		1	43	1	22	43
	Q 4 weeks		1	57	1	29	57
	Q 5 weeks		1	71	1	36	71
Visit Window (Days)				±7	±3	±3	±3
Activity							
Informed consent		X					
Inclusion/exclusion criteria check		X			X		
MCC confirmation		X			X		
SARS-CoV-2 antigen test*		X	X	X	X	X	X
Medical history		X					
Demography		X					
Pregnancy test c		X			X		
FSH level d		X					
Physical examination e		X	X	X	X	X	X
Vital sign measurements f		X	X	X	X	X	X
12-lead ECG(s) g		X				X	X
SIB risk and monitoring h		X	X	X	X	X	X
Samples for safety laboratory tests		X	X	X	X	X	X
Samples for SLE panel i		X					

	IVIg Dosing Frequency	SCN a	IVIg Dependency b		IVIg Monitoring c		
Visit (Days)		Up to 28 days	IDV1 d	IDV2 b	IMV1 f	IMV2	IMV3
	Q 2 weeks		1	29	1	15	29
	Q 3 weeks		1	43	1	22	43
	Q 4 weeks		1	57	1	29	57
	Q 5 weeks		1	71	1	36	71
Visit Window (Days)				±7	±3	±3	±3
Activity							
Samples for urinalysis		X					X

	IVIg Dosing Frequency	SCN Error! Reference source not found.	IVIg Dependency b		IVIg Monitoring c		
Visit (Days)		Up to 28 days	IDV1 d	IDV2 e	IMV1 f	IMV2	IMV3
	Q 2 weeks		1	29	1	15	29
	Q 3 weeks		1	43	1	22	43
	Q 4 weeks		1	57	1	29	57
	Q 5 weeks		1	71	1	36	71
Visit Window (Days)				±7	±3	±3	±3
Activity							
Samples for pharmacodynamics j			X	X	X	X	X
Samples for immunogenicity k		X					
Biomarkers l					X	X	X
Virology screen		X					
Pharmacogenetic sample		X m					

	IVIg Dosing Frequency	SCN Error! Reference source not found.	IVIg Dependency b		IVIg Monitoring c		
Visit (Days)		Up to 28 days	IDV1 d	IDV2 e	IMV1 f	IMV2	IMV3
	Q 2 weeks		1	29	1	15	29
	Q 3 weeks		1	43	1	22	43
	Q 4 weeks		1	57	1	29	57
	Q 5 weeks		1	71	1	36	71
Visit Window (Days)				±7	±3	±3	±3
Activity							
Research sample r					X o	X s	X s
IVIg administration p			X	X	X	X	X
Grip strength a		X	Continuous Monitoring				
MMN-RODS		X	X	X	X	X	X
mMRC		X	X	X	X	X	X
9-HPT		X	X	X	X	X	X
HRPQ					X	X	X
EQ-5D-5L					X	X	X
CAP-PRI					X	X	X
FSS					X	X	X

9-HPT=9-Hole Peg Test; ANA=antinuclear antibody; BMI=body mass index; CAP-PRI=chronic acquired polyneuropathy patient-reported index; C-SSRS=Columbia- suicide severity rating scale; DBTP=double-blinded treatment period; dsDNA=double stranded DNA; ECG=electrocardiogram; ENA=extractable nuclear antigen antibodies; EQ-5D-5L=Euro-Quality of Life 5 Dimensions 5 Levels; FSH=follicle-stimulating hormone; FSS=fatigue severity scale; ██████████  
 HRPQ=Health-Related Productivity Questionnaire; IDV=IVIg dependency visit; IMP=investigational medicinal product; IMV=IVIg monitoring visit; INR=international normalized ratio; IVDP=IVIg dependency period; IVIg=intravenous immunoglobulin; IVMP=IVIg monitoring period; MCC=MMN Confirmation Committee; MMN=multifocal motor neuropathy; MMN-RODS=Rasch-built overall disability scale for MMN; mMRC=modified Medical Research Council; NAb=neutralizing antibodies; ██████████  
 PD=pharmacodynamic(s); PE=physical examination; PHQ-9=patient health questionnaire 9 depression questionnaire; Q=every; SCN=screening period; SIB=suicidal ideation and behavior; SLE=systemic lupus erythematosus; SNP=single nucleotide polymorphism; TSQM=Treatment Satisfaction 14-item Questionnaire for Medication

Note: All assessments will be performed before IVIg administration unless otherwise specified.

\* **For Germany only:** A SARS-CoV-2 rapid antigen test must be completed or a negative rapid antigen test not older than 48 hours (depending on local requirements) must be presented upon site entry for each visit. The antigen test must be negative before the visit can begin. Rapid antigen testing will only be mandatory if required locally.

- a The screening period is 1 to 28 days before the IVMP or the IVDP. The scheduled time of visit is variable based on the participant's IVIg dose regimen retrieved from their medical record (inclusion criterion 5.1a). The screening period may be extended by an additional 14 days to a total of 42 days with the written approval of the medical monitor.
- b The IVDP, if applicable, occurs up to 15 weeks (105 days) before the IVMP.
- c The IVMP occurs up to 11 weeks before day 1 of the DBTP.
- d IDV1 will coincide with the participant's regularly scheduled IVIg administration.
- e Participants will have an earlier visit than planned if they demonstrate a clinically meaningful deterioration between the scheduled visits of the IVDP. This visit will be considered IDV2.
- f IMV1 will coincide with the participant's regularly scheduled IVIg administration and will be the participant's next regularly scheduled IVIg visit after IDV2 if they entered the IVDP. The visit window for IMV1 is not applicable if the participant does not enter the IVDP.
- g Female participants will have a serum pregnancy test performed at screening. A urine pregnancy test will be performed at IMV1 for women of childbearing potential.
- h FSH levels will be measured at screening for all female participants.
- i The PE will include the parameters specified in Section 8.2.1 of the protocol.
- j Weight, height, and BMI calculation will be performed at screening. Weight will also be measured at IMV3 and used to calculate the dose for all IMP administrations.
- k Triplicate 12-lead ECGs will be performed during screening and at V1. A single 12-lead ECG will be performed at all other scheduled time points.
- l The C-SSRS will be used to assess the risk of suicidal ideation at screening. SIB risk monitoring will be based on question 9 of the PHQ-9 at all other scheduled time points.
- m An ANA test will be performed at screening, the titer and staining pattern will be reported; the potential presence of ENA autoantibodies (anti-dsDNA, anti-Smith, anti-phospholipid (anti-cardiolipin IgG and anti-beta-2-glycoprotein IgG), anti-Ro (anti-Ro52 and anti-Ro60), anti-La and anti-U1RNP) will be evaluated from the blood samples collected. The presence of ENA autoantibodies will only be reported if ANA  $\geq 1:100$ .
- n Samples should be collected before IVIg is administered.
- o Immunogenicity assessments will be performed predose of IVIg administration.
- p [REDACTED]
- q A blood sample for SNP analysis will be collected at this time point.
- r Samples must be collected before IVIg is administered.
- s A research sample will be collected during the IVIg monitoring period (visits IMV1-IMV3). This sample should be collected predose and postdose of the IVIg administration. This sample should be collected immediately after the end of the IVIg administration, regardless of the duration (after the last hour or day) of the administration.
- t IVIg will be administered during the IVIg dependency and IVMP at the time points scheduled. IVIg may be administered over several days according to the local standard of care. All IVIg administrations must occur within the specified visit windows.
- u Grip strength will be measured on-site at all study visits and monitored daily starting from the IVDP or IVMP.
- v Adverse events and concomitant medications/procedures will be monitored continuously from receipt of informed consent signature until the last study-related activity. All available vaccination history should be recorded.

